### **Sample size justification:**

We propose a total sample size  $N = 54$  completed participants. To estimate an effect size for this study, we examined multiple prior data sets. First, our prior laboratory-based data on effects of EFT on delay discounting and ad-libitum food intake and on effects of remotely delivered EFT on dietary intake and BMI revealed generally “large” effect sizes ( $f > .40$ ). However, due to the uncertainty with which similarly large effect sizes would be observed for each of the broad range of additional measures used in the present study (e.g., medication adherence), we chose to power the proposed study for a more conservative, “medium” effect size of  $f = .25$ . Using this effect size, our power analysis indicated 54 total participants would be required based on an ANOVA model with group (EFT/control) as a between-subjects factor, time as a within-subjects factor, as well a group x time interaction. This analysis was performed in G\*Power 3.1, a type 1 error rate of  $\alpha = 0.05$ , correlation between repeated measures of .50, 95% statistical power. This provides 95% power to detect effects of EFT on lab-based measures assessed at baseline and follow-up assessments (e.g., HbA1c, BMI).

#### **Data analysis:**

We will use repeated measures ANOVA to examine changes in delay discounting, glycemic control, dietary intake, physical activity, medication adherence, BMI, and body composition (Specific Aim 1), as well as acceptability of the intervention (Specific Aim 2) in subjects who are randomly assigned to EFT and control conditions. Covariates will be included, as appropriate, including gender and socioeconomic status.

We will test for attrition bias by comparing participants who drop out versus those who complete the study. We will use intention to treat methods, and include all randomized subjects. We have a rigorous retention plan but expect up to 15% attrition. We will use maximum likelihood-based procedures to impute missing data. This approach is associated with more accurate parameter estimates than other approaches (e.g., last-observation carried forward), and is appropriate even when missing data are not missing at random

Statistical review was conducted by: **[name]** (name of statistician)  
**Fralin Biomedical Research Institute** (Department/Institution of statistician)

If no statistical review was done, explain why:

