**Inclusion Criteria:**

- age 18 or over
- type 2 diabetes diagnosis
- prescribed or recommended oral glucose-lowering medication for type 2 diabetes
- HbA1c level of ~8% or greater
- body mass index of 25 or greater

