**-Laboratory Assessment Sessions (Weeks 0, 8, 16, and 24)**

At assessment sessions, we will collect measures of blood HbA1c, blood pressure, height, and weight. Participants will also complete delay discounting tasks, food purchase tasks, and complete other study questionnaires (e.g., demographics).

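### The plan names repeated measures ANOVA for outcomes taken at up to four lab visits but states no covariance structure or sphericity correction; used uncorrected on all four visits, the group x time test would run at roughly 6-8% instead of 5% under plausible assumed correlations

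*Combined protocol and SAP*

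**What the plan says.** Item 24, Data analysis, gives one method for all outcomes: "We will use repeated measures ANOVA to examine changes in delay discounting, glycemic control", followed by the other Aim 1 measures and acceptability. Covariates are to be added as appropriate. The same section promises an intention-to-treat analysis of everyone randomized, expects up to 15% attrition, and plans maximum likelihood handling of missing data without naming a model.

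Item 24, Sample size justification, sets out the ANOVA with group between subjects, "time as a within-subjects factor, as well a group x time interaction". Its inputs are f = .25, alpha = .05, "correlation between repeated measures of .50" and "95% statistical power". From these, "our power analysis indicated 54 total participants would be required". The number of time levels is not given; the paragraph claims power for "effects of EFT on lab-based measures assessed at baseline and follow-up assessments (e.g., HbA1c, BMI").

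Item 22 lists "Laboratory Assessment Sessions (Weeks 0, 8, 16, and 24"), at which HbA1c, weight and delay discounting are taken. Diet and physical activity are assessed three times. Item 31 adds brief online assessments, with delay discounting as an example, at Weeks 3, 9 and 15.

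Nowhere does the plan mention a sphericity check, an epsilon correction, a covariance structure, the visits that enter the model, or the contrast that decides the primary outcomes.

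**The concern.** The univariate F test for group x time is exact only if every pairwise difference between visits has the same variance (sphericity). A common correlation with equal variances satisfies this, and it is the only pattern the plan mentions. Visits eight weeks apart, during and after a weight-loss programme, are unlikely to follow it: neighbouring visits usually correlate more than distant ones, and the spread of weight change tends to grow as people diverge. The test then has fewer effective degrees of freedom than it uses, and it rejects a true null too often.

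Both primary outcomes, delay discounting and glycemic control, are measured at all four lab visits, so both are exposed if all four are analysed together. The silence also leaves the choice between a corrected and an uncorrected p-value, and the choice of visits, open until the data are seen.

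**Working it through.** **Inputs.** From item 24: N = 54, f = .25, alpha = .05, r = .50, group x time model. From item 22: m = 4 visits for lab measures, m = 3 for diet and activity. Assumed: 27 per arm (the allocation ratio is not stated), complete data, no true effect, and each covariance pattern below.

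**Step 1: the plan's own figure.** For the within-between interaction with k = 2 groups, G*Power uses lambda = N m f² / (1 - r), df1 = (k - 1)(m - 1) and df2 = (N - k)(m - 1).

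- m = 2: lambda = 54 x 2 x .0625 / .50 = 13.5 on 1 and 52 df, power .9501. The smallest N is 54, an exact match.
- m = 3: the smallest N is 44. m = 4: it is 36. Neither matches.

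So the sample size was computed for two time levels. With two levels there is one difference score per person and sphericity cannot fail.

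**Step 2: epsilon.** Let S be the visit covariance, C = I - J/m (J the all-ones matrix) and A = CSC. Then epsilon = (tr A)² / [(m - 1) tr(A²)]. It equals 1 under sphericity and is at least 1/(m - 1), which is 1/3 for four visits.

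Worked case: first-order autoregressive (AR(1)) with r = .8, equal variances, m = 4.

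- The entries of S sum to 4 + 2(3 x .8 + 2 x .64 + .512) = 12.384, so tr A = 4 - 12.384/4 = .904.
- The squared entries sum to 10.0027. The row sums are 2.952, 3.24, 3.24 and 2.952, and their squares sum to 38.4238.
- tr(A²) = 10.0027 - (2/4) x 38.4238 + 12.384²/16 = .376.
- epsilon = .904² / (3 x .376) = .72.

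Random-slope case: slope variance per visit interval equal to the residual variance. With visit times 0, 1, 2, 3 the centred sum of squares is 5, so the non-zero eigenvalues of A are in ratio 1 : 1 : 6. Then epsilon = 8² / (3 x 38) = .56. The random intercept drops out.

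**Step 3: type I error.** Under the null, F is distributed as (N - 2) x (sum of w_i times chi-square on 1 df) / (sum of w_i times chi-square on N - 2 df), where w_i are the non-zero eigenvalues of A. The uncorrected test compares F with the 95% point on (m - 1) and (N - 2)(m - 1) df; the corrected test multiplies both df by epsilon. Simulated with at least 400,000 draws per pattern:

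| Visits | Assumed covariance | epsilon | Uncorrected | Corrected (true epsilon) |
|---|---|---|---|---|
| 4 | common r = .50 | 1.00 | 5.0% | 5.0% |
| 4 | AR(1) .5 | .86 | 5.8% | 4.9% |
| 4 | AR(1) .7 | .77 | 6.3% | 4.8% |
| 4 | AR(1) .8 | .72 | 6.6% | 4.8% |
| 4 | AR(1) .9 | .68 | 7.0% | 4.9% |
| 4 | AR(1) .8, SD 1, 1.5, 2, 2.5 | .60 | 7.5% | 4.8% |
| 4 | random slope, 1 : 1 : 6 | .56 | 7.9% | 4.9% |
| 3 | common r = .50 | 1.00 | 5.0% | 5.0% |
| 3 | AR(1) .5 to .95 | .92 to .81 | 5.3-5.9% | 4.8-5.0% |
| 2 | any | 1.00 | 5.0% | 5.0% |

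The theoretical ceiling, at epsilon = 1/(m - 1), is 10.9% for four visits and 8.5% for three. With 46 participants (54 less 15%) the four-visit AR(1) .8 figure is 6.7%, so attrition in itself changes little.

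**Step 4: does the HbA1c entry threshold add to this?** Item 21 requires "HbA1c level of ~8% or greater". Truncating a normal baseline at its population mean of 8.0, on top of a common correlation of .50, lowers epsilon only to .985, with error 5.1%. At common correlations of .7 to .9 the error is 5.0-5.1%. On top of AR(1), truncation raises epsilon, from .72 to .77 at r = .8 and from .68 to .71 at r = .9, and the error falls slightly (6.6% to 6.2%, and 6.9% to 6.7%). The threshold is not a separate cause.

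**The case against.** The strongest reply is that the plan is silent on correction, and silence is not a decision to use none. Most software prints a corrected p-value beside the uncorrected one, and reporting it would be consistent with the text. The planned maximum likelihood handling of missing data also points away from a classical complete-case ANOVA. And N = 54 fits two time levels only, so the test that was powered may be one in which the problem cannot arise.

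Most of this stands. A reader might infer that the plan prescribes an uncorrected test on all four visits, that both primary outcomes are therefore certainly tested at an inflated level, or that the inflation has a known size. The documents support none of these. They give no epsilon, and their one stated correlation yields exactly 5.0%. A reader might also infer that the HbA1c eligibility threshold breaks sphericity by design; Step 4 shows that it does not.

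What remains is the omission. The two-level power calculation does not show that only two visits will be analysed, and if two were meant, the plan does not say which. The Background section says outcomes are assessed during and just after the intervention and again at six months, to estimate short- and long-term effects, which suggests more than two. The maximum likelihood sentence names no model or covariance, so it does not settle the matter.

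**Conclusion.** The point holds conditionally. If all four lab visits enter one uncorrected repeated measures ANOVA, and correlation between visits decays or variance grows with time, the group x time test exceeds its nominal 5%. The excess is about 0.8 to 2 percentage points under AR(1) correlations of .5 to .9 and about 3 points under the random-slope pattern, which suits weight or BMI (not primary outcomes) better than the primary ones. Diet and activity, with three assessments, gain at most about 0.9 points under AR(1). A two-time-point comparison is unaffected. All these figures assume 27 per arm, complete data and covariances that the documents do not supply.

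The direction of the error is clear, its size modest, and the remedy nearly free. It is a cheap improvement, not a flaw that undermines the trial.

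**What to change.** In item 24, Data analysis, for every outcome with three or more assessments, replace the ANOVA with a likelihood-based linear mixed model: group, visit and group x visit as fixed effects, unstructured visit covariance, Kenward-Roger degrees of freedom, all randomized participants included. Four visits need 4 x 5 / 2 = 10 covariance parameters, which 54 participants should support. This model needs no sphericity assumption, uses every observed visit, and fits the commitments already made to intention to treat and maximum likelihood.

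In the same place, state which visits enter for each outcome (for delay discounting, whether the online assessments count) and which single group x time contrast decides each primary outcome.

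If ANOVA is kept, state that every test with more than one time degree of freedom rests on the Greenhouse-Geisser corrected p-value, and fix this before any outcome data are seen.

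The cost is a few sentences and slightly larger p-values; no new data or participants are needed. By the Step 1 formula, with df and lambda multiplied by epsilon and f = .25, 95% power over four visits needs 42 participants at epsilon .8, 48 at .7 and 60 at .5. So 54 still suffices under mild to moderate departures, although f = .25 over four visits does not describe the same effect as over two.

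### The plan imputes missing outcomes by maximum likelihood and tests by repeated measures ANOVA, with no step carrying imputation uncertainty; read as a single fill-in, it either inflates type 1 error or shrinks the EFT effect.

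*Combined protocol and SAP*

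**What the plan says.** All of the relevant text is in Section III, item 24.

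- **Model.** "We will use repeated measures ANOVA to examine changes in delay discounting, glycemic control, dietary intake, physical activity, medication adherence, BMI, and body composition". The same sentence covers intervention acceptability under Aim 2. Item 19 names delay discounting and glycemic control as the primary outcomes.
- **Analysis set.** "We will use intention to treat methods, and include all randomized subjects".
- **Expected loss.** "We have a rigorous retention plan but expect up to 15% attrition".
- **Missing values.** "We will use maximum likelihood-based procedures to impute missing data". The plan prefers this to carrying the last observation forward, on grounds of more accurate parameter estimates, and says that it "is appropriate even when missing data are not missing at random".
- **Error rate.** The sample size justification sets alpha at 0.05, with a correlation of .50 between repeated measures.

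The plan does not say whether imputation is single or multiple, which variables enter it, or how the variance of the imputed values reaches the F test. Item 22 schedules four laboratory visits (Weeks 0, 8, 16 and 24), but item 24 does not say which of them enter the ANOVA.

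**The concern.** Standard repeated measures ANOVA needs a complete row for each participant. A plan that keeps everyone randomized and uses that ANOVA must fill the gaps first, and imputation is the step the plan names for this. A likelihood-based fill-in replaces a missing value by its prediction. That prediction has no residual scatter of its own, and its regression coefficients are estimated. If the ANOVA then counts it as a measurement, the error variance is too small and the degrees of freedom too large.

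The direction of harm depends on a choice the plan leaves open. If the imputation model contains arm, the arm difference among the filled values repeats the one seen in the observed values, so the same information is counted twice and the test rejects too often. If it omits arm, dropouts in both arms receive values from one common regression, and the estimated difference is pulled toward zero.

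Neither problem needs informative dropout. Both arise when data are missing completely at random, so this point is separate from the plan's claim about data not missing at random. What is at stake is the only analysis stated for the two primary outcomes.

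**Working it through.** **1. The plan's own figure.** For the group x time test with k = 2 groups and m time points, the noncentrality is f² × N × m / (1 − rho), with (k − 1)(m − 1) and (N − k)(m − 1) degrees of freedom. With f = .25, N = 54, m = 2 and rho = .50 this is 0.0625 × 54 × 2 / 0.5 = 13.5 on 1 and 52 df, and power is 0.950. N = 53 gives 0.946. So 54 reproduces with two time points (m = 3 would give 44, m = 4 would give 36).

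**2. Inputs.** From the plan: alpha 0.05, rho .50, 54 completers, attrition up to 15%. Assumed here: 64 randomized (54/0.85 = 63.5, rounded up), 1:1 allocation, normal data with unit variance, and rho = .70 as a second value.

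**3. Two visits, single fill-in, arm in the imputation model, dropout completely at random at rate d.** The test compares mean change between arms. Per participant:

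- variance that the ANOVA sees: (1 − d) × 2(1 − rho) + d × (1 − rho)²
- true variance in large samples: (1 − rho)² + (1 − rho²)/(1 − d)

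At rho = .50 and d = .15:

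- seen: 0.85 × 1 + 0.15 × 0.25 = 0.8875
- true: 0.25 + 0.75/0.85 = 1.1324
- ratio: 1.1324/0.8875 = 1.276
- effective critical value: 1.96/√1.276 = 1.735
- two-sided error: 8.3%

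| rho | d | seen | true | ratio | type 1 error |
|---|---|---|---|---|---|
| .50 | .05 | 0.9625 | 1.0395 | 1.080 | 5.9% |
| .50 | .10 | 0.9250 | 1.0833 | 1.171 | 7.0% |
| .50 | .15 | 0.8875 | 1.1324 | 1.276 | 8.3% |
| .70 | .05 | 0.5745 | 0.6268 | 1.091 | 6.1% |
| .70 | .10 | 0.5490 | 0.6567 | 1.196 | 7.3% |
| .70 | .15 | 0.5235 | 0.6900 | 1.318 | 8.8% |

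**4. Simulation of the same case** (20,000 trials per setting, N = 54 and 64, rho .5 and .7):

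- 15% attrition: 8.3-8.8% when dropout is completely at random, 8.6-9.5% when it depends on baseline.
- 10% attrition: 6.8-8.0%.
- 5% attrition: 5.9-6.5%.
- At N = 64, rho = .5 and 15%, the mean reported standard error is 0.233 against a true 0.267, which is 13% too small (1 − 0.233/0.267). Coverage of the 95% interval is 91.5%.

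**5. Three or four visits** (4,000 trials per setting, N = 64, rho .5, 15% final attrition, completely random dropout, arm used in the imputation):

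- dropout spread over visits: 8.8-9.9%
- everyone leaves after baseline: 10.2-12.1%
- only the last visit missing: 6.9-8.8%

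**6. Single fill-in with arm omitted.** Type 1 error is 4.6-5.2% with two visits and 4.7-5.4% with three or four. The filled 15% carry almost no arm difference, so a true effect of 0.50 SD becomes about 0.85 × 0.50 = 0.425. Simulation gives 0.42.

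**7. Methods that carry the uncertainty.** Multiple imputation with arm in the model (20 imputations, Rubin's rules), two visits and 15% attrition: 4.7-5.4%. Direct likelihood on the observed data, four visits: 4.9%.

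Simulation error is about ±0.4 points for two visits and ±1 point for three or four.

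**The case against.** The strongest objection is that the plan never says the filled values are analysed as if observed. Its argument for more accurate parameter estimates is the language of likelihood estimation, so the sentence may be loose wording for direct (full-information) likelihood. Multiple imputation is not excluded either. Both keep the error rate near 5%. This stands: fill-in followed by ANOVA is the most literal reading, but it is not the only one. Against it, direct likelihood imputes nothing, the one alternative the plan names is itself a single fill-in method, and no mixed model or combining rule is mentioned.

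A reader might go further and infer that the stated 0.05 error rate is not delivered. The documents do not support that. Inflation needs both a single fill-in and arm in the imputation model, and the plan states neither. Nor is 15% a forecast: it is an upper limit, set beside a retention plan and a $100 completion bonus (item 31) meant to limit missing data.

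A reader might also add that the ANOVA violates sphericity over four visits. That is a separate matter, and it would rest on an assumed correlation pattern and an assumed absence of correction. The sample size reproduces with two time points, where sphericity does not arise.

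**Conclusion.** The point holds in conditional form. The primary analysis is not specified closely enough to fix its error rate, and its most literal reading performs worse than a standard alternative whichever way the imputation model is built. With a single fill-in and arm in the model, type 1 error is about 8-10% at 15% attrition for two visits or for dropout spread over visits, about 6-8% at 5-10% attrition, and about 7-12% at 15% over several visits, depending on timing. With arm omitted, error stays near 5% and the EFT effect is understated by roughly the missing fraction, 0.50 SD becoming about 0.42.

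The figures rest on 64 randomized, 1:1 allocation and normal data, none of which the plan states. If direct likelihood or multiple imputation is what the investigators intend, the error rate is about 5% and only the wording is at fault.

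**What to change.** Replace the imputation and ANOVA sentences in item 24 with one of these:

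- **Mixed model (simplest).** Analyse each continuous repeated outcome by a likelihood-based mixed model for repeated measures, fitted to all observed visits of all randomized participants, with arm, visit and arm x visit, and with no values filled in.
- **Multiple imputation.** If imputation is preferred, use multiple imputation with arm in the imputation model, list the other variables in it, and combine the results by Rubin's rules.

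If either was already intended, one sentence saying so closes the point. The change is to wording only and uses standard software. The cost is that p-values and intervals will be slightly less favourable than under a single fill-in with arm in the model.

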#### **-Diet, activity, and weight self-monitoring (Weeks 1-16).**

Participants will be taught how to record food, drink, exercise, and at home weight measurements in MyFitnessPal (see Appendix C: Study Websites). MyFitnessPal is a smartphone and web based app that tracks diet and exercise and can record the number of calories, macro and micronutrients consumed. Participants will be asked to use MyFitnessPal for self-monitoring throughout the study, recording the amount and types of food they eat and activity they engage in, as well as their weights. User accounts will be created for participants and will not include any identifying information.

At the end of the intervention period (approximately Week 16), participants may retain access to MyFitnessPal through Week 24 to continue self-monitoring of diet, exercise, and weight. However, participants will not be required to use this software during this period.

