**\*\*\*If this study is a retrospective record review only, you may skip to Section VII\*\*\***

31. Will subjects receive any compensation or gifts to participate?

Yes       No       N/A

- If yes, specify payment amount, how it will be prorated and how payment will be made: **Participants may receive up to \$300 for completion of all study procedures, as follows.**
  - **Assessment Session 1 (Week 0): \$20**
  - **Assessment Session 2 (Week 8): \$30**
  - **Assessment Session 3 (Week 16): \$35**
  - **Assessment Session 4 (Week 24 follow-up, post-intervention): \$40**
  - **Physical Activity and Diet Assessments 1-3 (Weeks 0, 8, and 16): \$20 per assessment week (\$60 total possible). These will occur outside the laboratory. At each assessment, participants will be asked to wear the Actigraph accelerometer to measure physical activity for a period of seven days. On three of those days, participants will also be asked to complete the ASA-24 dietary recall questionnaire online.**
  - **Brief Online Assessments (Weeks 3, 9, and 15). \$5 per assessment (\$15 total possible). Participants will be asked to complete brief online assessments (e.g., delay discounting, food purchasing) outside of the laboratory. EFT+BT participants will also be asked to complete an EFT event/cue-generation exercise.**
  - **Participants will also receive an additional bonus at Week 24 of \$100 for completing 90% or more of all assessment sessions and at-home assessments (Actigraph, brief online assessments, and diet recalls). The magnitude of this bonus was chosen in order to motivate attendance at the follow-up assessments for the majority of participants and thus minimize the occurrence of missing data, including from those participants who may have been less successful in the intervention or follow-up period.**

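### The missing-data plan gives no role to the online delay discounting scores and home weights that the trial collects, which could reduce dropout bias for one primary outcome and for weight

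*Combined protocol and SAP*

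**What the plan says.** Section III, item 24 (Data analysis) plans repeated measures ANOVA on all randomized participants, a comparison of dropouts with completers, and an expected attrition of up to 15%. For missing values it says "We will use maximum likelihood-based procedures to impute missing data", and adds that this remains suitable when data are not missing at random. The only covariates named are gender and socioeconomic status. No auxiliary variable is named.

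Elsewhere the document collects two outcomes remotely:

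- **Delay discounting**, a primary outcome in item 19. At Weeks 3, 9 and 15, under Section V, item 31: "Participants will be asked to complete brief online assessments (e.g., delay discounting, food purchasing) outside of the laboratory". Laboratory sessions are at Weeks 0, 8, 16 and 24 (item 22).
- **Weight.** Item 22, self-monitoring in Weeks 1-16: "Participants will be taught how to record food, drink, exercise, and at home weight measurements in MyFitnessPal". After Week 16 this is optional. The data list in item 23 has weight from a digital scale and does not mention the MyFitnessPal weights.

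HbA1c, the measure of the other primary outcome, is taken only at laboratory sessions.

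**The concern.** If only laboratory values enter the model, a missed Week 16 visit is predicted from visits at Week 8 and earlier. A setback after Week 8 is then invisible, and the predicted value is too favourable. The Week 15 online score is one week from the visit and could show the setback, as could a recent home weight.

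This matters for the comparison when such losses differ between arms. If they occur mainly in control, the control mean looks too good and the EFT effect is understated. If they occur mainly in the EFT arm, the effect is overstated.

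The document gives some reason to expect the situation. Item 26 names travel to the sites as a cost to participants. Item 31 justifies the 100-dollar bonus partly by the wish not to lose participants who did less well. A participant who skips a visit but still answers online is therefore plausible, although no rate is given.

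The plan's remark about data not missing at random adds to the concern. Standard likelihood methods need missing at random, so the quality of the conditioning variables matters.

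**Working it through.** **1. The plan's own figure.** Item 24 proposes "We propose a total sample size $N = 54$ completed participants", from an "ANOVA model with group (EFT/control) as a between-subjects factor, time as a within-subjects factor", with "correlation between repeated measures of .50, 95% statistical power", f = 0.25 and alpha 0.05. The number of time points is not stated; m = 2 is inferred because it returns 54.

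- Noncentrality: lambda = f² × N × m / (1 − rho) = 0.0625 × 54 × 2 / 0.5 = 13.5.
- With 1 and 52 degrees of freedom, power = 0.9501, so 54 is reproduced.
- Implied difference in change: sqrt(13.5 × 4 / 54) = 1.0 SD.
- Randomized number for 54 completers at 15% attrition: 54 / 0.85 = 63.5, so 64, or 32 per arm. Expected loss is 32 × 0.15 = 4.8, about 5 per arm.

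Nothing in this point changes the sample size.

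**2. What has to be assumed.** From the plan: correlation 0.50 between laboratory visits and 15% missing. Not in the documents, so assumed: a true effect of 0.50 SD, the dropout mechanism, the correlation between the online score and the Week 16 value, and the share of dropouts who still report online. Outcomes have unit SD and higher is worse. Dropout is outcome-related in control and random in the EFT arm. The estimate is normal-theory maximum likelihood for the Week 16 group difference, fitted by arm.

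**3. Size of the estimated effect (truth 0.50 SD).**

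| Control dropout follows | Correlation | Dropouts still reporting | Lab-only | With online score | Gain |
|---|---|---|---|---|---|
| online score | 0.80 | all | 0.42 | 0.51 | 0.09 |
| online score | 0.80 | half | 0.41 | 0.45 | 0.04 |
| online score, steeply | 0.80 | all | 0.36 | 0.50 | 0.14 |
| Week 16 value | 0.95 | all | 0.41 | 0.49 | 0.08 |
| Week 16 value | 0.95 | half | 0.41 | 0.45 | 0.04 |
| Week 16 value | 0.70 | half | 0.41 | 0.43 | 0.02 |
| Week 16 value | 0.95 | none | 0.41 | 0.41 | 0 |

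The rows on the Week 16 value are 0.50 minus the simulated bias: 0.09 without the online score, and 0.01, 0.05, 0.07 and 0.09 with it.

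When dropout follows the Week 16 value steeply, with a correlation between 0.70 and 0.80, the laboratory-only estimate falls to about 0.31. It rises to about 0.39 if all dropouts report and to about 0.34 if half do. At a correlation of 0.60 with half reporting, the gain shrinks to about 0.01.

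**4. Other dropout patterns.**

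- Same outcome-related mechanism at 15% in both arms: bias is about zero with or without the online score.
- Outcome-related dropout of 20% against 10%, correlation 0.95: bias is about 0.06 SD without the online score. With it, bias is 0.01 (all report), 0.02-0.03 (half) or 0.06 (none).
- Random dropout: the standard error goes from 0.269 to 0.261 if all report, (0.269 − 0.261) / 0.269 = 3.0% smaller. If half report it goes from 0.266 to 0.263, 1.1% smaller.

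No figure is offered for weight, because the coverage of home weights and their agreement with the laboratory scale are unknown.

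**The case against.** The strongest reply is that the plan is only silent. Item 24 says delay discounting without restricting it to the laboratory, and the abstract in item 17 says outcomes are assessed both remotely and in the laboratory. The online scores could therefore already be repeated measures in the model. A reader might infer that the plan excludes them; the text does not say so. This stands. What remains is that the choice is open and could be made after the data are seen, and that the home weights are not even listed as study data.

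A second reply is that the bias is conjectural. It needs outcome-related dropout that differs by arm, and participants who miss visits yet keep reporting. The documents establish none of these. This also stands, and it makes the size of the bias conditional.

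A third reply is that full recovery in the table depends on the mechanism. It occurs only when dropout follows the online score itself and every dropout still reports, which makes the data missing at random given that score by construction. In the other settings recovery is incomplete. So the claim has to be partial reduction, not removal.

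Finally, coverage is limited. HbA1c has no remote counterpart, online discounting ends at Week 15, and home weights are optional after Week 16 and self-reported. These limits narrow the benefit but do not argue against using the readings where they exist.

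**Conclusion.** The point holds in a conditional form. The plan gives no stated role to remote readings of one primary outcome and of weight. If the model is laboratory-only and dropout is outcome-related and differs by arm, using the readings moves the estimate toward the truth by roughly 0.02-0.14 SD when the true effect is 0.50 SD. That range assumes correlations of 0.70 or more and that at least half of the dropouts still report. Otherwise the benefit is a slightly smaller standard error or nothing. In none of the differential-dropout settings shown did the auxiliary score make the bias worse.

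A reader might infer that the trial's EFT estimate will be biased, or that the remote data would repair any dropout problem. The documents support neither. They do not show differential dropout, and auxiliary variables make missing at random more plausible without making the method valid when it fails. The plan's assurance on that last point should not be relied on.

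**What to change.** In item 24, Data analysis, add wording such as: The likelihood or multiple-imputation model for missing laboratory values includes, as auxiliary variables only, the online delay discounting scores from Weeks 3, 9 and 15 for delay discounting, with their relation to the laboratory score allowed to differ by arm; and, where logged, the latest home weight before the missed visit for weight and BMI. The outcomes analysed remain the laboratory measurements.

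The arm-specific relation is needed because, under item 31, the EFT+BT group also does a cue-generation exercise at these online assessments, which may shift its scores.

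Add the MyFitnessPal weights to the data list in item 23. Replace the remark on data not missing at random with a statement that the method assumes missing at random given the variables in the model.

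The cost is a few sentences, one data export and slightly more analysis work. It needs no extra visit and no change to the sample size. The small downside is that home weights are self-reported and of unknown coverage, so they should serve only as predictors. The change does nothing for HbA1c and little for Week 24.
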